Subject Schedule

Subjects in the control arm will undergo all items except the prehabilitation intervention. Subjects in the treatment arm will undergo all items.

Intake Assessment

At this visit, subjects will meet with a member of the Physical Therapy staff who will perform an assessment of the subject's functional exercise capacity, mobility, and balance through the following:

- a. 6MWT
- b. TUG Test
- c. FSST
- d. Kansas City Cardiomyopathy Questionnaire

Other information collected by the research coordinator will be demographic information, subject contact information and comorbidities. Subjects will be randomized at the conclusion of the Intake Assessment.

Prehabilitation (treatment group only)

Based on the results of the Intake Assessment, the physical therapist will determine a course of conditioning specific to each subject; however, each subject will receive a minimum of eight visits and a maximum of 12 over the 3 to 5 weeks prior to the surgery date. Date and time of each visit will be collected. Providers will note the following adverse events that occur during conditioning:

- a. MACE
- b. Syncope, Falls and musculoskeletal adverse events
- c. Adverse events from other complications
- d. Serious adverse events, including those that require hospitalization

Pre-operative Assessment

The final encounter with the subject pre-operatively will perform the same assessments as performed during the Intake Assessment:

- e. 6MWT
- f. TUG Test
- g. FSST
- h. Kansas City Cardiomyopathy Questionnaire

TAVR procedure

Providers will implant the aortic valve and record the following:

- i. Type and size of valve used
- j. Adverse events during surgery

Discharge assessment

Upon discharge, the subject will be assessed for the following:

- k. Discharge disposition
- l. Length of stay in ICU (hours) and total hospital (days)
- m. Cost of stay (assessed by total charges accrued during hospitalization)

30-day Follow-up Assessment

All subjects' electronic health records (EHR) will be monitored for thirty days from the discharge date for the following:

- n. Comorbidities and study comorbidities
- o. Inpatient re-admission information
- p. Cost of stay (assessed by total charges accrued during a readmission hospitalization)
- q. Date and time of visit
- r. Syncope
- s. MACE
- t. Falls and musculoskeletal adverse events
- u. Adverse events from other complications
- v. Serious adverse events, including those that require hospitalization
- w. Mortality

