The subject will also perform the following:

- x. 6MWT
- y. TUG Test
- z. FSST
- aa. Kansas City Cardiomyopathy Questionnaire

1-year Follow-up Assessment

All subjects' electronic health records (EHR) will be monitored for one year from the discharge date for the following:

- a. Inpatient re-admission information
- b. Cost of stay (assessed by total charges accrued during hospitalization)
- c. Date and time of visit
- d. Syncope
- e. MACE
- f. Falls and musculoskeletal adverse events

- g. Adverse events from other complications
 - h. Serious adverse events, including those that require a readmission hospitalization
 - i. Mortality
- The subject will also perform the following:
- j. 6MWT
 - k. TUG Test
 - l. FSST
 - m. Kansas City Cardiomyopathy Questionnaire

Research procedures

Patients who qualify for TAVR will be screened by the research coordinator. The research coordinator will also review provider office visit schedules and maintain close contact with the TAVR program coordinator for potential study subjects. The patient will be screened thoroughly ensuring he/she meets all inclusion and exclusion criteria. Once the possible study patient has been identified then the research coordinator will approach the patient and verbally explain the study to them. Adequate time will be provided for questions and answers. The patient will be provided a written copy of the informed consent and time to read it. Once the patient signs the informed consent, the study procedures may commence. The first visit will be the Intake Assessment where the patient will meet with the physical therapist and research coordinator. This assessment will include the 6MWT, TUG test, FSST, KCCQ, patient demographics, subject contact information, and comorbidities. At the completion of this assessment, the patient can be randomized.

The patients randomized to the treatment arm will then be scheduled to begin the prehabilitation part of the study. Subjects will receive a maximum of 12 therapy visits over the next 3 to 5 weeks prior to the surgery date.

Below is a chart that describes what will occur at each required study visit.

	Intake Assessment	Prehabilitation (Treatment only)	Pre-operative Assessment	TAVR	Discharge Assessment	30-day Follow-up Assessment	1-year Post-operative monitoring
Demographics (MRN, name, date of birth, gender, payor, surgery date, surgery type, etc.)	X						
Subject contact information (preferred method, address, phone/text, e-mail, etc.)	X						

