Comorbidities (all diagnoses codes)	X					X	X
Study comorbidities 
 • Current medications • Pre-existing conditions related to reduced exercise capacity, mobility, and/or balance; including physical disabilities unrelated to aortic stenosis 	X					X	X

6MWT	X		X			X	X
TUG Test	X		X			X	X
FSST	X		X			X	X
Kansas City Cardiomyopathy Questionnaire	X		X			X	X
Date and time of visit		X	X			X	X
Adverse events		X	X*			X	X
• MACE							
• Syncope							
• Falls and musculoskeletal adverse events							
• Adverse events from other complications							
• Serious adverse events, including those that require hospitalization							
Type and size of valve used for TAVR				X			
Adverse events during surgery				X			
Discharge disposition					X		
Length of stay					X		
• In ICU (hours)							
• Total hospital (days)							
Cost of stay (assessed by total charges accrued during hospitalization)					X		
Inpatient readmission information						X	X

*This should be assessed in both groups prior to TAVR to see if the control arm experienced similar adverse events independent of prehab therapy.

Data analysis and Data Monitoring

Evaluate primary, secondary and the safety outcomes (as listed in the protocol) by conducting a data integrity check to assure reliability of the data. Once all data inconsistencies are corrected data analysis should occur. The analysis would compare 2 groups: the study group and the control. Based on the objectives, the data will be analyzed using the required statistical tests; categorical variables would be compared using the Fishers Exact test or Chi-square tests and measurement data would be compared using the independent sample t-test or Mann Whitney U test. All analysis will be evaluated using parametric tests unless the data is not normal in which case non-parametric tests will be used.

As needed interim analysis of primary, secondary and safety outcomes by study group (treatment vs. no treatment) will be conducted. If a decision is made to stop the study early, this limitation should be expressed in any project write-up. If at the conclusion of the assessment of the primary outcome (6 minute walk test) there is a significant difference between the study groups ($p < .05$) a Power analysis will be conducted, and if the Power is greater than 80%, a recommendation to conclude the study could be made – if this is done there is risk of making a type II error and should be shared in any project write up.

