Transcatheter Technologies (TCT) national meeting. Also, it is planned that the results will be submitted for publication in a peer –review scientific journal.

Delineation of resources required to conduct the study

The resources required to conduct this study include research coordinators and physical therapists. No special software, equipment, processes, or tests are needed to conduct this study.

ADVERSE EVENTS

Adverse Event

An Adverse Event (AE) is any untoward medical occurrence, unintended injury or untoward clinical signs in patients, users or other persons, related to the study.

Adverse events may be volunteered by patients, elicited by the Investigator or designee, or collected via observation by the Investigator. All AEs will be assessed by the Investigator who will determine whether or not the event is related to the study, and whether or not the event meets serious criteria. If it is determined that an AE has occurred, the investigator should obtain all the information required to complete the AE Form of the CRF. Source documents should be collected for each AE. In addition, patients will be instructed to contact the investigator, and/or study coordinator if any significant adverse events occurs between study visits.

Serious Adverse Event

An Adverse Event is considered serious if the event:

1. Leads to death;
2. Leads to a serious deterioration in the health of the study patient that:
 - Results in life-threatening illness or injury;
 - Results in a permanent impairment of a body structure or a body function;
 - Requires inpatient hospitalization or prolongation of existing hospitalization;
 - Results in medical or surgical intervention to prevent permanent impairment to body structure or a body function;
3. Significant medical event.

References

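### No scheduled both-arm item collects adverse events or deaths between the end of the TAVR procedure and hospital discharge

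*Combined protocol and SAP*

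**What the plan says.** The combined protocol and SAP sets out data collection twice: as text under Subject Schedule, and as a visit chart under Research procedures. Everything except the prehabilitation sessions applies to both arms.

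- **TAVR procedure.** Valve type and size, and "Adverse events during surgery".
- **Discharge assessment.** It opens "Upon discharge, the subject will be assessed for the following" and then lists disposition, ICU and hospital length of stay, and charges. It lists no safety event and no vital status.
- **30-day Follow-up Assessment.** Electronic records "will be monitored for thirty days from the discharge date for the following". The list includes syncope, MACE, falls and musculoskeletal events, other adverse events, serious adverse events and mortality.
- **1-year Follow-up Assessment.** Records "will be monitored for one year from the discharge date for the following", with the same event categories and mortality.
- **Visit chart.** The adverse-event row is marked at prehabilitation, pre-operative, 30-day and 1-year, and is blank at TAVR and at discharge. Mortality has no row.

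Other parts of the document point towards fuller coverage. Study design says that every subject is followed from intake to one year after the procedure, and the last chart column is headed "1-year Post-operative monitoring". The Adverse Events section describes reporting with no time limit, and its seriousness criteria include "Leads to death" and "Requires inpatient hospitalization or prolongation of existing hospitalization".

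**The concern.** The hospital stay straight after valve implantation is a period in which post-procedural events are of direct interest. The Objectives include the effect of prehabilitation on post-procedural clinical outcomes, and hypothesis 2b predicts that these improve. The Safety Outcomes list the same event categories that the follow-up windows collect, and the analysis section compares them between the two groups. If the schedule is followed literally, that comparison has no common check of every subject for the inpatient days. It depends on whatever is reported outside the schedule.

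Two consequences follow:

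- A death before discharge precedes both stated mortality windows. It also cuts the hospital stay short, and length of stay is a secondary outcome on which shorter is taken as better.
- The pilot is described as a precursor whose components will be used in a larger trial, so a gap in the schedule could be carried forward.

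The plan itself shows that equal ascertainment was wanted. The footnote to the chart asks for adverse events in both groups before TAVR, so that the control arm can be compared. The same reasoning applies after the procedure.

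**Working it through.** No arithmetic applies, and the plan gives no figure to reproduce. The check sets the schedule text beside the chart, interval by interval, for the listed safety events and for death.

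| Interval | Schedule text | Chart | Scheduled in both arms? |
|---|---|---|---|
| Intake to TAVR | Events during conditioning (treatment arm) | Adverse-event row marked at prehabilitation and pre-operative; footnote extends the latter to both groups | Yes |
| During TAVR | Intra-procedural adverse events | Separate row, marked at TAVR | Yes |
| End of TAVR to discharge | Disposition, length of stay, charges | Adverse-event row blank at TAVR and discharge | **No** |
| Discharge to 30 days | Event list and mortality, from discharge | Adverse-event row marked | Yes |
| Discharge to one year | Event list and mortality, from discharge | Adverse-event row marked | Yes |

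Text and chart agree on the omission. The uncovered interval is each subject's post-procedure hospital stay. It has two causes: the empty discharge cell and the discharge start of the windows.

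The next question is whether any other provision supplies a scheduled check for that interval.

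1. **Study design, follow-up statement.** It spans the interval, but it names no inpatient item, and its end point is counted from the procedure while the event windows are counted from discharge.
2. **Chart column headings.** The post-operative wording of the last column would allow a look back to the procedure. The text, however, fixes the start at discharge.
3. **Diagnosis codes.** The row "Comorbidities (all diagnoses codes" is marked at 30 days, so codes from the index stay might surface there. The text puts comorbidities inside the discharge-started 30-day list, so this is a secondary trace at most.
4. **Discharge disposition.** It might reveal a death, but the outcome is defined by the level of care needed. It would not reveal MACE, syncope or falls.
5. **DSMB.** It reviews adverse events that have been collected and schedules no collection.
6. **Adverse Events section.** Events may be volunteered, elicited or observed at any time, so this route does reach the inpatient days. It is not tied to a visit. Its definition of an adverse event is limited to occurrences related to the study, although the following paragraph has the investigator judge relatedness for all events. Staff who apply the definition literally could leave out an event that they attribute to the valve procedure.

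Item 6 is the only substantial route. It gives capture, but not the same check in every subject.

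**The case against.** The strongest reply is that the interval is not uncollected and only lacks a visit-specific entry. Subjects are followed continuously. Adverse-event reporting has no time limit and includes elicitation and observation. Death and prolonged hospitalization are serious by definition, and a DSMB sees all reported events. A subject who dies before discharge would also be noticed, because length of stay and disposition fall due at discharge, and the walk, mobility, balance and quality-of-life assessments fall due later. Finally, hypothesis 1 asks whether pre-procedural therapy is safe, and the schedule covers that period in both arms.

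Most of this stands. Most in-hospital deaths and serious events would probably be recorded, and a reader who inferred from the windows that they would be lost would be going beyond the documents. The reply does not supply a uniform check for events that are non-serious, or that staff regard as complications of the procedure. Those are part of the listed safety outcomes and of the clinical-outcomes aim.

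A second tempting inference is bias between arms. Discharge comes after randomization, and the plan hypothesises that prehabilitation brings it forward, so a window that opens at discharge could in principle open at different times in the two groups. The documents show the mechanism but no evidence that capture would differ by arm.

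**Conclusion.** The point holds as a gap in scheduled collection. In both arms, from the end of the procedure to discharge, no scheduled item collects MACE, syncope, falls, other adverse events, serious adverse events or mortality. This rests on reading the schedule and chart as written. Site staff may in practice look back to the procedure, but the text does not tell them to.

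Its size cannot be stated. The documents give neither an in-hospital event rate nor a rate of capture through unscheduled reporting, so any count of missed events among the 70 subjects would be an assumption. The likely loss is uniform capture of non-serious or procedure-attributed inpatient events. The six-minute walk primary outcome and the question of pre-procedural safety are not shown to be affected. The grade is minor to should-fix: the omission is clear and cheap to close, but a material loss of events is not demonstrated.

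**What to change.** 1. In the 30-day and 1-year assessments, start the windows for MACE, syncope, falls, other adverse events, serious adverse events and mortality at the date of the TAVR procedure. Keep collection running through at least 30 days after discharge and through one year.
2. Add one adverse-event and vital-status chart-review entry to the Discharge assessment and to the discharge column of the chart, in both arms. It should cover the listed event categories regardless of judged relatedness, and be completed for subjects who die in hospital.
3. Report in-hospital deaths by arm next to the length-of-stay results, so that a stay ended by death is not read as an early discharge.

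The cost is a modest chart review per subject. It covers several event categories and so is more than a tick box, but it falls where length of stay and charges are already being abstracted. There is no added visit and no change to clinical care.

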Although the effect of pre-procedural physical conditioning on TAVR patients has not been studied, there is significant evidence that pre-procedural physical conditioning, or “prehabilitation,” is beneficial to patients undergoing cardiac surgery. Pre-procedural conditioning has been shown to decrease both ICU and hospital length of stay in patients undergoing coronary artery bypass grafting surgery (CABG) as well as improve physical functioning after surgery.(10)(11) Additionally, a recent meta-analysis concluded that pre-procedural conditioning is effective at reducing postoperative complication rates and length of hospital stay after cardiac surgery.(12)

Patients with severe symptomatic aortic stenosis are at high risk for adverse cardiac event or death and they are advised to only perform activities requiring mild exertion. However, monitored exercise testing in these patients has been shown to be safe.(13,14) In addition, current guidelines recommend monitored exercise testing in patients with severe aortic stenosis and absent or equivocal symptoms.(15) As such, the modest exertion required for physical therapy in a monitored environment is predicted to carry a very low risk.

Decreased exercise capacity and high frailty scores have been shown to be a strong determinant of mortality and adverse events in patients with aortic stenosis. However, implementation of a systematic and monitored physical therapy program to improve exercise capacity and modify frailty scores prior to a major intervention such as TAVR has never been performed. Nor have the outcomes of such a monitored program been evaluated.

Objectives

In this pilot study, we aim to identify patients undergoing TAVR who are at elevated risk for adverse clinical events due to decreased exertional capacity and physical deconditioning. We aim to determine if monitored pre-procedural physical therapy is safe in these patients. Lastly, we aim to assess the efficacy of prehabilitation a) to improve physical functioning by the time of TAVR and to sustain benefit through 30 days post-procedure; and b) to determine its effect on post-procedural length-of-stay, clinical outcomes, and quality of life.

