As a precursor to a large, definitive randomized clinical trial, this pilot study will examine the components of patient recruitment and retention, assessment of exertional capacity, and program implementation of this intervention with the goal that they will be employed in a larger scale study and possibly to all TAVR programs in the United States. To this end, all components of this study were chosen not only for clinical efficacy, but also for cost effectiveness and ease of implementation into current “real world” TAVR programs.

Primary Efficacy Outcomes

- **Functional exercise capacity – Change in 6 Minute Walk Test (6MWT)**
Measure: Does prehabilitation improve the subject’s functional exercise capacity from first PT assessment to pre-procedure assessment and first PT assessment to one month post-procedure, as measured by the 6MWT?

Secondary Efficacy Outcomes

- **Mobility – Timed Up-and-Go (TUG) test**
Measure: Does prehabilitation improve the subject’s mobility from first PT assessment to pre-procedure assessment and first PT assessment to one month post-procedure, as measured by the TUG test?
- **Balance – Four Square Step Test (FSST)**
Measure: Does prehabilitation improve the subject’s balance from first PT assessment to pre-procedure assessment and first PT assessment to one month post-procedure, as measured by the FSST?
- **Discharge disposition**
Measure: Does prehabilitation make it less likely that a patient will require a higher level of care at discharge than they required prior to admission (for example, arrive from home and discharged to home)?
- **Length of stay in Intensive Care Unit (hours)**
- **Total hospital length of stay (days)**

- **Change in quality of life**
Measure: Does Kansas City Cardiomyopathy Questionnaire score change from first PT assessment to one month post-procedure?
- **30-day readmission**
Measure: Does the subject have a 30-day readmission post-procedure?

Safety Outcomes

- Syncope
- Major adverse cardiac events (MACE)
- Falls and musculoskeletal adverse events
- Adverse events from other complications
- Serious adverse events, including those that require hospitalization

Hypotheses

1. Monitored pre-procedural physical therapy is safe for patients identified as frail who are undergoing transcatheter aortic valve replacement.
2. Monitored pre-procedural physical therapy in patients to undergo transcatheter aortic valve replacement will result in:

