 - a. An objective improvement in patient physical function from baseline to the time of procedure and 30 days post-procedure.
 - b. Decreased length of stay and improved clinical outcomes and quality of life.

Study design

This is a pilot study involving a cohort of seventy subjects randomized to either participate (treatment group) or not participate (control) in a prehabilitation program prior to undergoing a TAVR. After providing informed consent, subjects will be randomized via REDCap™ to a treatment or control group. Thirty five subjects will be randomized to each group. Subject number and randomization will be assigned by REDCap™. All subjects in this pilot study will be followed from the intake assessment through one year post-procedure.

Study population and recruitment methods

The research coordinator will identify potential TAVR patients using clinic schedules and then conduct a chart review to verify that they meet inclusion/exclusion criteria. Patients will be approached by the research coordinator regarding the study. The research coordinator will verbally explain the study and provide time for questions and discussion. The patient will be provided with a written copy of the consent document to read and review. The research coordinator will set up an additional appointment to assess understanding and verify willingness to participate. The patient will then sign the consent if interested in participation.

Inclusion and exclusion criteria:

Inclusion Criteria

- Subject must be ambulatory (with or without an assist device)
- Subject has severe aortic stenosis and is felt an appropriate candidate for TAVR by the Heart Team.

- Subject requires 6.0 seconds or longer to complete a 15ft walk test
- Subject must be able to move between sitting and standing without assistance from another person.
- Subject has adequate iliac and femoral arterial anatomy to allow for TAVR via transfemoral access
- Subject is 18 years of age or greater
- Subject is willing to give consent and participate in the study

Exclusion Criteria

- Subject is incapable of following instructions
- Subject is unable to meet the minimum required physical therapy visits
- Subject has other medical conditions rendering it unsafe, in the opinion of the Principal Investigator and physical therapy staff, to perform a 6 Minute Walk Test or physical therapy conditioning prior to TAVR
- Subject has significant severe un-revascularized epicardial coronary disease.

Role of subjects

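### Change in 6MWT is to be compared by an unadjusted t-test, although intake 6MWT is measured before randomisation and ANCOVA on it would usually be more precise

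*Combined protocol and SAP*

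**What the plan says.** Primary Efficacy Outcomes asks whether prehabilitation improves "functional exercise capacity from first PT assessment to pre-procedure assessment and first PT assessment to one month post-procedure, as measured by the 6MWT". The same two windows apply to TUG and FSST under Secondary Efficacy Outcomes. For quality of life that section asks: "Does Kansas City Cardiomyopathy Questionnaire score change from first PT assessment to one month post-procedure".

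The analysis is set out in Data analysis and Data Monitoring. The two groups are compared, and "measurement data would be compared using the independent sample t-test or Mann Whitney U test". The choice between the tests is governed by one rule: "All analysis will be evaluated using parametric tests unless the data is not normal in which case non-parametric tests will be used". No covariate, regression or baseline-adjusted model is mentioned in any section.

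The four intake measures come before allocation. The Intake Assessment section says "Subjects will be randomized at the conclusion of the Intake Assessment", and Research procedures agrees: "At the completion of this assessment, the patient can be randomized". Study design gives 70 subjects, 35 per group, without an effect size, SD or design power.

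**The concern.** The plan does not say outright which variable enters the t-test, but the outcome is defined as change, so a t-test on change scores is the natural reading. That test subtracts the whole intake value from the follow-up value, which is the same as fixing the baseline slope at 1. If the true slope is below 1, as it usually is when a measurement is repeated with error, the subtraction over-corrects and adds noise. If raw follow-up values were meant instead, the slope is fixed at 0 and the intake value is not used at all. Either way, a valid pre-randomisation covariate is collected on every subject and never used as one.

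This matters because efficacy is a stated objective. The study aims to "assess the efficacy of prehabilitation a) to improve physical functioning by the time of TAVR and to sustain benefit through 30 days post-procedure", and 6MWT is the primary measure of that. With at most 35 per arm, precision is scarce, and the study is described as a precursor to a larger definitive trial, which would be planned from its estimates.

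**Working it through.** **Inputs from the documents.** 35 per arm, N = 70 (Study design); a 0.05 significance threshold (Data analysis and Data Monitoring), taken as two-sided because sidedness is not stated. There is no stated power figure to reproduce: 80% appears only in the rule on concluding the study early.

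**Assumptions.** The intake-to-follow-up correlation r, the ratio k of follow-up SD to intake SD, and the effect size are not in the documents. They are varied below.

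**Variance.** In units of intake variance:

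- change score: 1 + k² − 2rk
- ANCOVA: k²(1 − r²), times 1 + 1/(N − 4) for estimating the slope
- ratio, ANCOVA to change: [k²(1 − r²) / (1 + k² − 2rk)] × (1 + 1/66) at N = 70

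The bracket equals 1 − (1 − rk)² / (1 + k² − 2rk), so it never exceeds 1, and it reaches 1 only when the true slope rk is exactly 1. The average loss is therefore at most 1/66 = 1.5%.

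Example with a gain (k = 1, r = 0.5): 0.75/1.00 = 0.750; × 1.0152 = 0.761, a 23.9% reduction.
Example with a loss (k = 1.2, r = 0.8): 0.5184/0.5200 = 0.997; × 1.0152 = 1.012, a 1.2% increase.

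Reduction in the variance of the arm difference, N = 70 (negative = loss):

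| k | r = 0.5 | r = 0.7 | r = 0.8 | r = 0.9 |
|---|---|---|---|---|
| 1.0 | 23.9% | 13.7% | 8.6% | 3.6% |
| 1.1 | 17.0% | 6.5% | 1.7% | −1.5% |
| 1.2 | 11.6% | 1.9% | −1.2% | 0.8% |

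At k = 1 and r = 0.95 the reduction is 1.0%. A simulation of 20,000 trials with k = 1 gave variance ratios of 0.76, 0.87 and 0.96 at r = 0.5, 0.7 and 0.9, in line with the formula.

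**Restricted intake.** One entry criterion is "Subject requires 6.0 seconds or longer to complete a 15ft walk test", which may narrow the spread of intake 6MWT. Suppose this cuts intake variance to 64% while the slope and residual variance stay fixed. The ratio becomes (1 − r²) / [(1 − r²) + 0.64(1 − r)²] × (1 + 1/66). For r = 0.5: 0.75/0.91 × 1.0152 = 0.837, a 16.3% reduction. For unrestricted r of 0.7, 0.8 and 0.9 it is 8.8%, 5.2% and 1.8%.

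**Power.** Noncentral t, two-sided 0.05, for an assumed arm difference of 0.6 SD of change:

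| Setting | t-test on change | ANCOVA, r = 0.5 / 0.7 / 0.8 |
|---|---|---|
| 35 per arm, k = 1 | 69.7% | 80.9% / 75.9% / 73.5% |
| 35 per arm, k = 1.2 | 69.7% | 74.9% / 70.5% / 69.1% |
| 28 per arm (assumed 20% missing), k = 1 | 59.7% | 71.3% / 65.8% / 63.4% |

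**Non-normal errors.** Simulated power (20,000 trials per setting, 35 per arm, k = 1, shift of 0.6 SD of change, r = 0.5 / 0.7 / 0.8):

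| Errors | Mann-Whitney on change | ANCOVA |
|---|---|---|
| Normal | 67% / 67% / 68% | 81% / 76% / 73% |
| t with 3 df | 82% / 85% / 87% | 84% / 81% / 79% |
| Lognormal (sigma 0.8) | 87% / 91% / 93% | 83% / 79% / 77% |

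Type I error was 0.044 to 0.053 for the t-test, Mann-Whitney and ANCOVA in all nine settings. ANCOVA is therefore the better replacement for the t-test, but not for Mann-Whitney when the data are clearly non-normal.

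**The case against.** The strongest reply is that this is a preference for efficiency in a pilot. The planned test is valid, no error rate is affected and no stated power target is missed. That stands and limits the weight of the point, but it does not remove it: efficacy is among the objectives and the improvement is nearly free.

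Second, the same walk test repeated around a programme of 3 to 5 weeks could correlate above 0.8. At k = 1, power would then rise only from 69.7% to 71.2% at r = 0.9. This is fair. The largest gain shown, about 11 percentage points, needs r = 0.5 and equal SDs.

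Third, 1/66 is an average over randomisations. In 200,000 simulated allocations of 35 per arm, the cost of estimating the slope exceeded 1/66 in about 31% and exceeded 5.9% in 5%. This is true, and the bound should be read as unconditional. The costly allocations are those with large intake imbalance, where the change-score comparison is also furthest off unless the true slope is 1.

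Fourth, Mann-Whitney beats ANCOVA in five of the six non-normal settings above. This is accepted, and it is why that branch should stay.

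Fifth, the primary 6MWT p-value and a power analysis feed a possible recommendation to conclude the study. Changing the primary test changes both inputs. The early-conclusion paragraph would then simply refer to the new analysis.

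**Conclusion.** The point holds. The plan compares change in 6MWT without adjustment, although a valid pre-randomisation baseline is available for it and for TUG, FSST and KCCQ. This is a missed gain in precision in the t-test branch only. It is not a bias, and the Mann-Whitney branch is not criticised.

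The size cannot be fixed from the documents. For r between 0.5 and 0.8, the variance reduction at N = 70 is 24% to 9% with equal SDs, 16% to 5% under the restricted-intake assumption, and 12% to a 1% loss at k = 1.2. It is close to nil when the true slope is near 1. Possible gains are several times the average loss, which is capped at about 1.5%, so the change is worth making. It ranks low among recommended changes.

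**What to change.** In Data analysis and Data Monitoring, before any comparison by arm is made, replace the t-test for outcomes that have an intake value with text such as:

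> For 6MWT, TUG and FSST (intake to pre-procedure and intake to one month) and KCCQ (intake to one month), the arms will be compared by a linear model with treatment arm and the intake value of the same measure, reporting the adjusted mean difference with 95% CI. If the data are clearly non-normal, the Mann-Whitney U test on change will be the test, with the ANCOVA estimate reported alongside.

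This covers the 2 + 2 + 2 + 1 = 7 comparisons already listed and adds none: no one-year comparison and no pre-operative KCCQ comparison. The outcome can stay defined as change, because modelling change or the follow-up value with the intake covariate gives the same arm difference. ICU and hospital length of stay have no intake value and keep the planned tests. It would help to state in advance how non-normality is judged, and that the early-conclusion paragraph refers to this analysis. If a comparison by arm has already been made under the provision for interim analysis as needed, report the change as made after that look.

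The cost is two sentences, no new data and one degree of freedom per model. The average variance increase is at most 1/66 = 1.5% with 70 analysed, or 1/52 = 1.9% with an assumed 56.
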